**NUTRITIONAL STATUS ASSESSMENT OF PEDIATRIC CYSTIC
FIBROSIS PATIENTS AND EFFECT OF NUTRITION EDUCATION ON
NUTRITIONAL STATUS**

STUDY PROTOCOL DATE: 03.09.2021

Follow-up	EDUCATION GROUP	CONTROL GROUP
Meet	
 • Introduction, explanation of the purpose of the research, giving information about the practices and obtaining informed consent • Application of questionnaires and scales • Education for the family: How to keep a correct and proper record of food consumption? (Using Food & Food Photo Catalog) 	
 • Introduction, explanation of the purpose of the research, giving information about the practices and obtaining informed consent • Application of questionnaires and scales • Education for the family: How to keep a correct and proper record of food consumption? (Using Food & Food Photo Catalog)
1st Week	
Cystic Fibrosis Nutrition Education-I: The Importance of Healthy Nutrition, Carbohydrate, Fat, Protein, Vitamin-Minerals, Water.
 
 • Definition of healthy eating, • The importance of adequate energy and macro-micronutrient intake for CF patients, • Foods containing macro and micronutrients such as carbohydrate-fat-protein-vitamin-mineral 	
2nd Week	
Cystic Fibrosis Nutrition Education-II: Food Groups, Common Nutritional Problems by Age Groups and Solution Suggestions.
 
 • The four basic food groups and the nutrients they contain • Changelists in TÜBER • Common nutritional problems according to age groups and solution suggestions 	
3rd Week	
Cystic Fibrosis Nutrition Education-III: General Review and Frequently Asked Questions and Answers
 
 • Summary information about the first two trainings, • Recommendations on how children diagnosed with CF can increase their energy and fat intake • Things to consider about PERT treatment • Frequently asked questions and answers • Document sharing 	
1st month and 3rd month	
 • Application of questionnaires and scales • Collection of food records 	
 • Application of questionnaires and scales • Collection of food records

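### Does the study set out to judge nutritional status without measuring it?

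*Protocol*

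**What the plan says.** The protocol is a title, a date and one follow-up table. The title gives two aims. It begins "NUTRITIONAL STATUS ASSESSMENT OF PEDIATRIC CYSTIC", then continues "FIBROSIS PATIENTS AND EFFECT OF NUTRITION EDUCATION ON", and ends by repeating nutritional status: a description of that status, and the effect of education on it.

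Measurement appears in two rows of the table, with the same content in both groups:

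- **Meet row:** introduction and consent, "Application of questionnaires and scales", and training for the family on "How to keep a correct and proper record of food consumption".
- **Months 1 and 3 row:** the same questionnaire entry, and "Collection of food records".

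The rows for weeks 1 to 3 hold teaching for the education group and no measurement. Week 1 covers "The importance of adequate energy and macro-micronutrient intake for CF patients". Week 3 includes "Recommendations on how children diagnosed with CF can increase their energy and fat intake". No questionnaire or scale is named anywhere, and nutritional status is not defined.

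**The concern.** Intake is not the same thing as nutritional status. A reader who goes from the title to the table looks for weight, height, body mass index or a laboratory value, and finds none.

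The teaching sharpens the worry. Only the education group is told why intake matters and how to raise it, and its families then record that same intake. The record-keeping training is shared, which helps, but it comes before the sessions and so cannot rule out a change in recording that the sessions bring about. If self-report were the only evidence, a difference between groups could be part real and part recording, with nothing objective beside it.

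The stake would be real, because a body measure not taken at a contact cannot be recovered by the analysts. The absence of a statistical analysis plan is no answer either: what is measured at which visit normally belongs in the protocol.

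**Working it through.** **Count of the cells.** The table prints months 1 and 3 as one row, so there are 2 assessment rows × 2 groups = 4 cells.

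| Item | Meet (2 cells) | Months 1 and 3 (2 cells) | Total |
|---|---|---|---|
| Unnamed questionnaires and scales | 2 | 2 | 4 of 4 |
| Food records collected | 0 | 2 | 2 of 4 |
| Objective measure listed | 0 | 0 | 0 of 4 |

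Splitting the shared row by contact gives 3 × 2 = 6 and hence 0 of 6. That is the same fact with one row counted twice.

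**What the count can show.** The zero would point to a design gap if the table itemised other measures and left these out. It does not. The teaching is set out topic by topic, while all assessment is reduced to one generic phrase. Named instruments number 0, and eligibility, sample size, allocation and outcome definitions are absent as well. A list with no named items is weak evidence that any one item was excluded.

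**Title against table.** A contradiction would need the title to require something that the table rules out. The title does not define nutritional status. Dietary assessment is part of assessing it, and an unnamed form can carry weight and height. The two passages are compatible.

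**Whether the recording argument bites.** It needs an analysis that rests on recorded intake alone. The document states no such analysis: questionnaires and scales appear in all 4 cells, and food records are not called the main outcome.

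**What an added z-score comparison could settle.** The document supplies no inputs, so n, SD and correlation are all assumptions here. Take SD = 1, baseline-adjusted comparison, two-sided 5%, df = 2n − 3:

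- residual SD = √(1 − r²)
- SE = residual SD × √(2/n)
- 95% half-width = t × SE

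| n per group | r | Residual SD | SE | Half-width | Power for 0.2 | Power for 0.1 |
|---|---|---|---|---|---|---|
| 20 | 0.80 | 0.600 | 0.190 | 0.38 | 0.18 | 0.08 |
| 30 | 0.90 | 0.436 | 0.113 | 0.23 | 0.42 | 0.14 |
| 50 | 0.95 | 0.312 | 0.062 | 0.12 | 0.89 | 0.35 |

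The extremes pair the smallest n with the lowest r and the largest n with the highest r, so the spread is wide by construction. Only the most favourable setting gives good power for 0.2, and none does for 0.1. A null result would usually leave open whether a difference in recorded intake was real.

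**The case for a change.** The best case for a change is that the title states a central outcome, the visit schedule is the place to list how it is measured, and no objective measure is listed. Acting would be cheap: one line naming the form that holds weight and height, or a narrower wording of the aim. Body measures would also serve the descriptive first aim, which does not depend on power to detect a difference between groups. Reading scales as weighing scales does not rescue the table, since paired with questionnaires the word most naturally means rating instruments.

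Much of this stands. The listing is incomplete, and a fuller table would help a reader. What does not stand is the step from not listed to not measured. The warning that a missed measurement is lost for good applies only if it was missed, and the document gives no ground for saying so. The cheapness of the remedy points the same way: if one line naming an existing form would answer the concern, it is about documentation and not about design.

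The Meet row also lists no collection of a food record. That is a separate question about a baseline for intake, and it does not bear on whether body measures were taken.

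**Conclusion.** No change to the plan follows. The observation is correct as a statement about listing: 0 of 4 assessment cells name an objective measure, and 0 instruments are named. It is not evidence of a wrong or contradictory design, because the table itemises no assessments at all and the title leaves nutritional status open.

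This conclusion rests on one judgement: that a team assessing nutrition in children with cystic fibrosis records weight and height, on a form or in the clinic, without the summary table having to say so. If that proved false, the results could still be reported honestly as effects on recorded intake and questionnaire scores. No size of bias can be given, since the document has no sample size, standard deviation or stated analysis. The power figures are illustrative only and carry no weight beyond showing that a short-term z-score comparison would often not decide the matter.

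### Does the schedule assign families to Education or Control before they consent and complete the baseline scales?

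*Protocol*

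**What the plan says.** The document consists of one follow-up table. Its two column headings, "EDUCATION GROUP" and "CONTROL GROUP", run over every row, including the first contact, Meet.

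The Meet row lists three items in each column, in the same order:

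- the consent step comes first, worded as "Introduction, explanation of the purpose of the research, giving information about the practices and obtaining informed consent";
- the baseline measurement comes second, given only as "Application of questionnaires and scales";
- training in record-keeping comes third, under "Education for the family: How to keep a correct and proper record of food consumption", taught with a photo catalogue.

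The next row, 1st Week, opens the teaching with "Cystic Fibrosis Nutrition Education-I" in the Education column and leaves the Control cell empty. The 2nd and 3rd Week rows follow the same pattern. The last row, "1st month and 3rd month", again has the same content in both columns: questionnaires and scales, and collection of food records.

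The table mentions no allocation, randomisation, concealment or blinding, and gives no sample size or allocation ratio.

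**The concern.** The title announces a study of the effect of education, which is a causal aim, and a causal reading depends on how the two groups came about. Taken from top to bottom, the table shows a family under a group heading at first contact, consenting there and filling in its baseline scales there. Nothing that forms groups appears between that point and the first lesson.

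If the group really were known at Meet, three things could go wrong:

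- **Entry.** Families could accept or decline according to the arm on offer, and staff could steer recruitment.
- **Baseline reports.** Questionnaire answers could be coloured by knowing whether teaching will follow. Adjusting for a baseline distorted in that way would not repair the comparison.
- **Follow-up.** The outcomes listed are questionnaires, scales and family-kept food records, and the arms differ visibly in weeks 1 to 3. A difference at month 1 or month 3 would then be hard to credit to the teaching alone.

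Allocation is part of trial conduct and belongs in a protocol, so an unseen statistical analysis plan does not explain its absence. It is reasonable to ask the question.

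**Working it through.** The issue is the order of steps, so the check is to set the rows side by side.

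| Row | Education column | Control column | Same content? |
|---|---|---|---|
| Meet | information and consent; scales; food-record training | information and consent; scales; food-record training | yes |
| 1st Week | first lesson | empty | no |
| 2nd Week | second lesson | empty | no |
| 3rd Week | third lesson | empty | no |
| 1st and 3rd month | scales; food records collected | scales; food records collected | yes |

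**Two orders of events, each tested against the table.**

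1. *Group set before Meet.* Every cell can be carried out as listed. Nothing in the table supports this order except that the column headings extend over the Meet row.
2. *Group set after Meet and before week 1.* Every cell can again be carried out as listed. Both future arms receive the same three items, and the first activity that needs a known group is the first lesson.

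Both orders fit, so the table does not choose between them. Schedules laid out by arm often show common visits under both headings simply because both arms attend them. The identical Meet cells sit easily with that convention and give no sign that families are handled differently by group before week 1.

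**What a known group could cost, under assumed values.** The document gives no standard deviation, correlation, sample size or effect size, so these inputs are illustrative only. Let d be the difference between groups at entry and r the correlation of the entry value with follow-up, both in SD units with equal SDs at the two times. The bias of an unadjusted follow-up comparison is then r × d.

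- r = 0.5, d = 0.3: 0.5 × 0.3 = 0.15 SD
- r = 0.7, d = 0.3: 0.7 × 0.3 = 0.21 SD
- chance allocation after Meet, expected d = 0: r × 0 = 0

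The first two lines require that the group was known at entry, that this knowledge changed who entered, and that the follow-up comparison is unadjusted. The document states none of the three. The third line requires that the allocation in the second order is by chance, which the document does not state either.

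**The case for a change.** The strongest argument for acting is that the schedule spells out the content of each lesson yet omits the step on which its causal aim rests. Staff who work from the table have no instruction to keep the group unknown until baseline is complete, and one added line before week 1 would supply it at almost no cost. Food records add to the worry: they are listed for collection only at months 1 and 3, so on the face of the table an intake imbalance at entry could not be seen.

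Part of this stands. The table has no allocation step, the timing is unstated, and assignment before consent cannot be ruled out from the text.

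The rest does not carry the point further. Leaving a step out is different from prescribing it in the wrong place, and no cell would have to be disobeyed to allocate after Meet. If allocation already happens there, an added line would alter the drawing and not the trial. The food-record point is a separate matter: the table teaches record-keeping at Meet and does not say which days the collected records cover. A 1:1 ratio or stratification by age band would be a preference. Lessons that discuss problems by age do not make stratification necessary, and the document gives no sample size or age range against which to judge it.

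**Conclusion.** The concern does not hold as a fault in the plan. That families are grouped before consent and baseline is an inference from column headings, and the identical Meet cells fit later allocation equally well. What is left is a gap in a one-table document, which a competent team fills in the ordinary way: take consent, complete the scales, allocate, then start teaching. That sequence obeys every line of the schedule.

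The size of any bias cannot be obtained from the document. The 0.15 to 0.21 SD range shows what would be at stake under assumed inputs and is not an estimate for this trial.

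The conclusion assumes that groups are formed by chance after Meet or, if they are not, that the report says so and describes the result as an association. Evidence that families or staff knew the group at first contact would reopen the question, but the document contains none.

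### Does teaching only the education group how to raise energy and fat intake, before any listed food record is collected, undermine the intake comparison?

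*Protocol*

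**What the plan says.** The protocol is a single follow-up table with one column per group.

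- **Meet row, both groups, same content.** Families hear an "explanation of the purpose of the research", complete questionnaires and scales, and are taught "How to keep a correct and proper record of food consumption", with a food photo catalog as the aid.
- **1st Week row, education group only.** The session includes "The importance of adequate energy and macro-micronutrient intake for CF patients".
- **3rd Week row, education group only.** The session includes "Recommendations on how children diagnosed with CF can increase their energy and fat intake".
- **Control cells for weeks 1 to 3.** Empty.
- **Row "1st month and 3rd month", both groups.** Questionnaires and scales are applied again, and the row lists "Collection of food records". This is the only row that lists collection.

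The title asks about the effect of education on nutritional status. The table does not name recorded intake as an outcome, does not rank outcomes and gives no sample size.

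**The concern.** A food record kept by the family is a self-reported measurement, and here the intervention can act on the reporter as well as on the child's diet. By month 1, families in the education group have been told why adequate energy intake matters and how to increase energy and fat. Control families have not. An education family might record more fully, or lean towards what it now knows to be desirable, without the child eating differently.

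The shared training at the Meet visit should even out recording skill. It comes before the teaching, though, and cannot even out what one group learns afterwards. The desirability route also has a direction: it pushes reported energy and fat upwards in the education group, in favour of the intervention. Unlike chance imbalance, it does not shrink as the sample grows. If it were large, a comparison of recorded intake could show a benefit of education that is partly an artefact.

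**Working it through.** **Order of events.** Read down the two columns, the sequence is:

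1. Meet: recording is taught to both groups.
2. Weeks 1 to 3: the value of adequate intake and ways to raise it are taught to the education group only.
3. Months 1 and 3: records are collected from both groups.

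So both listed collections follow the education-only sessions. Collection is not the same as recording, however. Families learn to keep records at the first visit, and the table does not say which days the month 1 records cover. Some of those days could precede the week 3 session. What is established is that collection follows the teaching, not that all recording does.

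**Possible size.** The protocol has no figure to reproduce, so every input here is an assumption: *n* = 20, 30 or 40 per group, a pure reporting shift of *d* SD with no true difference in intake, and a two-sided 5% two-sample t-test. The test statistic then follows a noncentral t distribution with 2*n* − 2 degrees of freedom and noncentrality *d*√(*n*/2). The rejection probability is P(|T| > t₀.₉₇₅).

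Worked case, *n* = 30 and *d* = 0.2: noncentrality = 0.2 × √15 = 0.775; degrees of freedom = 58; critical value = 2.002; rejection probability = 0.119.

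| Assumed shift (SD) | n = 20 | n = 30 | n = 40 |
|---|---|---|---|
| 0 | 0.050 | 0.050 | 0.050 |
| 0.1 | 0.061 | 0.067 | 0.073 |
| 0.2 | 0.095 | 0.119 | 0.143 |
| 0.3 | 0.152 | 0.208 | 0.263 |
| 0.4 | 0.234 | 0.332 | 0.424 |

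The arithmetic is sound, but it would hold for any bias in any two-group trial of these sizes. It runs from no effect to a serious one, and the document offers nothing to place this trial within it.

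**Would a change help?** Each candidate is set against the mechanism, which is desirable reporting by the family:

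- *Scripted review of each record with the family at collection, in both groups.* This addresses omitted items and portion sizes, that is, completeness. It does not address knowledge of the wanted answer, and questioning by study staff could prompt more desirable answers.
- *Comparing reported energy divided by predicted requirement.* The ratio only rescales reported energy. A high value in the education group looks the same whether it comes from over-reporting or from the rise in intake that the sessions aim at.
- *Sensitivity analysis excluding implausible records.* This selects on something measured after the education. Dropping high ratios could remove real responders from one group and so introduce a bias of its own.
- *Removing the group label before nutrient coding.* This guards against the coder, not the family.
- *Calling the result reported intake.* This is accurate wording, but it changes no result.

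**The case for a change.** The strongest case for acting is that the exposure is built into the schedule. The order of contacts is fixed by this table, not by a statistical analysis plan, and food records are one of only two assessment items listed at follow-up. The direction of the possible bias favours the intervention, and with an assumed 0.2 SD shift the nominal 5% error would be about two to three times too high (0.095 to 0.143). That other education trials share a weakness does not excuse a plan from reducing it where this is cheap.

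Much of this stands. The sequence is as described, the mechanism is plausible, and the common training does not remove it. Two steps fail. First, the argument needs a remedy that reduces desirability bias, and none of those examined does so demonstrably; one could do harm. Second, the lack of a check at collection is inferred from silence. The table gives no operating detail for any item and does not even name the questionnaires and scales. Collection procedures, coder masking and plausibility screening may well be set out in working procedures or in a statistical analysis plan that is not at hand.

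**Conclusion.** No change to the plan is needed. The contrast that creates the risk is the question the trial asks: one group is educated and the other is not. Measuring diet through family-kept records is a fair trade-off in such a trial, and its known cost is that a group difference in recorded intake may contain some difference in reporting.

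The size of that part is unknown. Under the assumed 20 to 40 per group and assumed shifts of 0 to 0.4 SD, the false-positive rate would lie anywhere from 5% to 42%, and a shift of 0.1 SD or less would matter little. The caveat applies only to conclusions drawn from the food records; the document does not make recorded intake the main outcome.

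Analysts can handle this in the ordinary way, by describing any such difference as one in reported intake and reading it beside any objective measure of nutritional status that the trial already collects. Coding the records without the group label is optional good practice against coder bias only. This conclusion rests on the one-table protocol as shown. It would be worth reopening if recorded intake proved to be the sole basis for the trial's main claim.

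### Is the one-month assessment too soon after the last education session to serve as an outcome time?

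*Protocol*

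**What the plan says.** The Protocol consists of one follow-up table with a single time column serving both groups: a first meeting, weeks 1, 2 and 3, and a final row headed "1st month and 3rd month". The title sets the aim as the "EFFECT OF NUTRITION EDUCATION ON" nutritional status.

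The sessions are given to the education group only:

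- Week 1 includes "The importance of adequate energy and macro-micronutrient intake for CF patients" and the foods that supply those nutrients.
- Week 2 deals with food groups and exchange lists, and includes "Common nutritional problems according to age groups and solution suggestions".
- Week 3, headed as a general review, opens with "Summary information about the first two trainings" and then lists "Recommendations on how children diagnosed with CF can increase their energy and fat intake", points on enzyme replacement, common questions and document sharing.

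The final row has the same two entries for each group: "Application of questionnaires and scales" and "Collection of food records". The table does not say from which event the months are counted or which days a food record covers. It names no primary outcome and no primary time point.

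**The concern.** The table runs from the first meeting through weeks 1 to 3 to the months, so the natural reading counts months from the first meeting. The third session is also the only one that lists explicit advice on raising energy and fat intake. If it falls on day 21, month 1 follows it by little more than a week, too short for a child's nutritional status to change. A food record handed in then might reflect little beyond families' recall of fresh advice.

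Because the two follow-up times share a row, one could read them as outcome times of equal weight. The trial would then have two chances of a positive result, one of them at a time when a real effect on status is unlikely.

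Counting from the end of education seems to offer no escape. Controls have no sessions and so no matching event, and if only the education group were counted from that event, the groups would be assessed at different times since the first meeting. Were all this so, a favourable month-1 result could be mistaken for an effect on nutritional status.

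**Working it through.** The Protocol gives no interval in days, so there is no figure of its own to reproduce. The check is calendar arithmetic plus a reading of what each row contains.

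**Assumptions.** First meeting = day 0; week 1 = days 1–7, week 2 = days 8–14, week 3 = days 15–21; one month = 28–31 days; three months = 84–92 days; sessions one week apart, so the third is 14 days after the first.

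**Gap from the third session = assessment day − session day.**

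| Months counted from | Gap to month 1 (days) | Gap to month 3 (days) |
|---|---|---|
| First meeting | 28 − 21 = 7 to 31 − 15 = 16 | 84 − 21 = 63 to 92 − 15 = 77 |
| First session | 28 − 14 = 14 to 31 − 14 = 17 | 84 − 14 = 70 to 92 − 14 = 78 |
| End of education | 28 to 31 | 84 to 92 |

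A gap of about one week needs both the first meeting as origin and a session at the end of week 3 (day 21: 28 − 21 = 7 to 31 − 21 = 10 days). The full range is 7 to 31 days.

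**Gap from the earlier sessions, counting from the first meeting** (the origin least favourable to the plan):

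- First session: 28 − 7 = 21 to 31 − 1 = 30 days before month 1.
- Second session: 28 − 14 = 14 to 31 − 8 = 23 days before month 1.

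The intervention under test is the three-session programme. Adequate energy intake is a topic from week 1 and practical suggestions are given in week 2; the third session partly repeats both. Exposure therefore does not begin in week 3.

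**What is measured at month 1.** Questionnaires, scales and food records. Recorded intake can change within days. The row names no slow measure, such as weight or height, for which one to two weeks would plainly be too short.

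**Standing of the two times.** The two visits share a row and have identical entries. That is how a visit schedule is compacted. Nothing there states a success rule, pools the times or declares them co-primary.

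**The arm-specific origin.** If only the education group were counted from the end of education, the groups would differ by 21 days: 21/30 = 70% of a one-month and 21/90 = 23% of a three-month follow-up. At an assumed growth of 2 to 3 kg per year this is 2 × 21/365 = 0.12 kg to 3 × 21/365 = 0.17 kg, most of which age-standardised z-scores would remove. The table has one time column for both groups, so nothing in it points to such a scheme. That origin would also put month 1 four weeks after the third session, which removes the complaint about a short gap.

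**The case for a change.** The strongest reply is that a visit schedule belongs in the protocol and cannot be left to an analysis plan. The title promises an effect on nutritional status, the explicit energy and fat advice comes last, and on the plain reading month 1 follows it by one to two weeks. The starting point for the months is open, and so are the days a food record covers; a month-1 record could fall just after the third session or even reach back before it. Counting from the first meeting in both groups and resting the main conclusion on month 3 would cost only wording.

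Part of this stands. The starting point and the record days are indeed unstated, and month 3 is the more informative time for the title's aim. But an early reading followed by a later one is an ordinary design, and calling month 1 a process measure is a preference between acceptable options. The choice of primary time point and any handling of multiplicity are commonly set in a statistical analysis plan. None is among the documents, so their absence here cannot be held against the Protocol. The single time column gives a sensible common origin for both groups. Even at the shortest gap of 7 days, a record would have to reach back more than a week before the visit to include days before the third session. The claim that reporting effects peak at month 1 has no support in the document.

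**Conclusion.** The concern does not hold. Nothing in the table is shown to be wrong or contradictory. Month 1 is an early assessment, 7 to 16 days after the third session on the plain reading and up to 31 days after it on another, with the first two sessions earlier still. It collects measures that can respond in that time, on the same schedule as a concurrent control group. Month 3 supplies the later assessment, 63 to 92 days after the third session across the origins considered. Equal standing of the two times is inferred from a shared row, and the 21-day difference between groups is hypothetical.

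This rests on the calendar assumptions above and on reading the single time column as common to both groups. The unstated origin of the months and the unstated food-record days are small gaps in detail that the table's layout lets an analyst fill sensibly; neither calls for a change to the design.

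### No food record is secured before the education starts: collection is scheduled only at months 1 and 3, and the days covered are not stated

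*Protocol*

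**What the plan says.** The protocol is a single follow-up table with one column for the education group and one for the control group.

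- **Meet (both groups).** Besides introduction and consent, the entries are "Application of questionnaires and scales" and a training item, "Education for the family: How to keep a correct and proper record of food consumption". No record is collected in this row.
- **Weeks 1 to 3 (education group only; the control cells are empty).** The sessions run from "Cystic Fibrosis Nutrition Education-I" to "Cystic Fibrosis Nutrition Education-III". Week 1 includes "The importance of adequate energy and macro-micronutrient intake for CF patients"; week 3 includes "Recommendations on how children diagnosed with CF can increase their energy and fat intake".
- **Months 1 and 3 (both groups).** The questionnaires and scales are applied again, and the table adds "Collection of food records".

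The number of recording days, their type and the period they belong to are not given anywhere.

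**The concern.** The questionnaires and scales have a measurement before education and two after it. The food record is the only listed follow-up measure without an entry before education, although its training takes place at Meet. A site could follow the table to the letter and hold no record of what any child ate before the first session.

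The sessions deal with energy and nutrient intake, so recorded intake measures directly what is taught. Without a baseline record, a change in recorded intake cannot be estimated, and a difference in recorded intake between the groups at the start can be neither checked nor adjusted for. How serious this is depends on how the groups are formed, which the document does not state. Under randomisation the cost is precision; otherwise it is bias. When data are collected is settled by the protocol, and no analysis plan can recover a record that was never kept.

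**Working it through.** **Order of events.** The plan has no figure to reproduce, so the first check is a count along the table.

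| Row | Education session | Food-record activity |
|---|---|---|
| Meet | none | training only |
| 1st Week | I | none |
| 2nd Week | II | none |
| 3rd Week | III | none |
| 1st month and 3rd month | none | collection at each time point |

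Scheduled collections before the first session: 0. After the last session: 2. Recording days specified: none. The order is the same whether month 1 is counted from Meet or from the end of education.

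**Size.** The document gives no sample size, correlation or allocation method, so every input below is an assumption:

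- correlation ρ between baseline and follow-up recorded intake: 0.3 to 0.7;
- pre-existing group difference, for the non-randomised case: 0.3 SD;
- group size, for the error rate: 30 per group.

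*Case 1: randomised groups.* The comparison at follow-up is unbiased. Adjusting for a baseline record multiplies the variance of the group difference by 1 − ρ². The equivalent gain in sample size is 1/(1 − ρ²), and the confidence-interval width is multiplied by √(1 − ρ²).

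| ρ | 1 − ρ² | Variance cut | 1/(1 − ρ²) | √(1 − ρ²) |
|---|---|---|---|---|
| 0.3 | 0.91 | 9% | 1.10 | 0.954 |
| 0.5 | 0.75 | 25% | 1.33 | 0.866 |
| 0.7 | 0.51 | 49% | 1.96 | 0.714 |

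The intervals would be about 5% to 29% narrower.

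*Case 2: groups not randomised, no education effect.* With equal SDs and a common within-group regression on baseline, the difference carried into the follow-up comparison is ρ × 0.3 SD. For a two-sample t-test with 30 per group (58 degrees of freedom, critical value 2.002), the non-centrality parameter is bias × √(30/2) = bias × 3.873. The rejection rate is the sum of both tails of the non-central t distribution.

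| ρ | Bias (SD) | Non-centrality | Rejection rate (nominal 5%) |
|---|---|---|---|
| 0.3 | 0.09 | 0.349 | 6.4% |
| 0.5 | 0.15 | 0.581 | 8.8% |
| 0.7 | 0.21 | 0.813 | 12.6% |

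**The case against.** The strongest reply is that collecting is not the same as recording. The row fixes when records are handed in, not when they are kept. Families are trained at Meet, before any education, so they may start recording at once, and what is handed in at month 1 may include days before the first session. This stands as a possibility, and it would be wrong to say that no baseline record can exist. But the table neither asks for such a record nor names the days, so none is secured.

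Second, the unnamed questionnaires at Meet may contain an intake measure. If so, it would be repeated with the same instrument at months 1 and 3 and could also serve as a balance check or covariate. That would soften the loss and make the figures above an upper picture of it. It would still be a different instrument from the food record, and nothing in the document shows that it is there.

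Third, no endpoint is named. The title speaks of nutritional status, and the rank of recorded intake is unknown. This is fair: the gap touches one measure and not every comparison in the trial. Its importance is inferred from the content of the sessions.

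Fourth, the sizes rest on assumptions, and the bias case needs non-randomised groups, which the document does not state. In that case adjustment for an imperfectly measured record might also leave some bias behind. Both points hold, so the figures serve only as illustration.

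**Conclusion.** The concern holds. As written, the schedule secures no food record before education in either group and leaves the days of the later records open. The finding rests on the order of the rows and needs no assumed number.

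The consequence is limited to recorded intake and depends on allocation: lost precision if the groups are randomised, possible bias if they are not. The sizes shown depend on the assumed correlation, the assumed 0.3 SD difference and the assumed 30 per group. The point should be fixed before enrolment, because the loss cannot be repaired for a family once its education has begun. Confidence is medium, because a record before education may be intended but not written down.

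**What to change.** Add a row for both groups between Meet and 1st Week, for example: *Food record kept after the Meet training and collected before Education-I; same window in the control group.* Require the same number and type of days as at months 1 and 3, and state for every record which days it covers. Name this record as the baseline covariate in the comparison of recorded intake at months 1 and 3. If a record before education is already planned, it is enough to state when it is kept and when it is collected.

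The cost is one more record per family to keep and one more to code; the training and the photo catalog are already provided at Meet. The first session has to wait until the record is handed in, which matters if Meet and week 1 are only a few days apart. Control families, who have no listed contact in weeks 1 to 3, need a way to hand theirs in.
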